4.4. Virology

4.4.1. Viral Phenotype

The JNJ-63623872 EC₅₀ and Oseltamivir IC₅₀ with their fold change values will be analyzed at baseline and at the subject's last study visit (FC = fold change in EC₅₀ (IC₅₀) value).

- The last study visit is defined as the last time point for which an EC₅₀ and/or IC₅₀ result is available.
- FC is calculated as the EC₅₀ (or IC₅₀) divided by the reference. If the patient EC₅₀ (or IC₅₀) is censored, the fold change value get the same censor, e.g. patient EC₅₀ = >20 nM, reference EC₅₀ = 4nM, Fold Change value >5.

The following output will be provided overall and by influenza subtype category:

- Emerging phenotypic resistance: descriptive statistics for FC in EC₅₀ and IC₅₀ value for JNJ-63623872 and oseltamivir respectively at baseline and the last study visit. The number (%) of subjects by treatment arm with censored phenotype data at baseline and the last study visit will also be shown.
- Descriptive statistics for fold change ratio of last study visit versus baseline including geometric mean and 95% CI.
- A listing showing viral load data together with phenotype data (EC₅₀, IC₅₀ and fold change values) per subject and influenza subtype for all available time points including screening/baseline.

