7. Time to improvement of vital signs.
8. Time to improvement of respiratory status.
9. Improvement on the ordinal scale.
10. Time to hospital discharge.
11. The time to influenza viral negativity based on qRT-PCR and/or viral culture from nasal MT swabs and, if applicable, based on PCR-based rapid molecular testing from nasal MT swabs.
12. Viral load over time and the rate of decline in viral load during treatment as measured by qRT-PCR and/or viral culture.

13. AUC of viral loads as measured by qRT-PCR and/or viral culture.
14. Resistance testing will be performed on all baseline samples as well as on qRT-PCR-positive post-baseline samples. Genotypic assays (sequencing of full length PB2 and other gene segments if applicable) will be used to determine resistance against JNJ-63623872. Phenotyping may be done at the sponsor's discretion. Resistance testing for neuraminidase inhibitors will also be performed as applicable.

Exploratory Endpoints

1. Length of ICU stay for subjects transferred to the ICU after baseline will be collected.
2. Use of antibiotics and/or corticosteroids during hospitalization.
3. Number of subjects admitted to the ICU.
4. Correlation between the decline in viral load (measured by qRT-PCR and/or viral culture) and changes in clinical symptoms.
5. PK/pharmacodynamic (PD) relationship (efficacy and safety).

An independent data monitoring committee (IDMC) will be established to monitor safety and efficacy data on a regular basis.

An interim analysis may be performed to support regulatory activities.

Pharmacokinetic Analyses

Descriptive statistics will be calculated for plasma concentrations of JNJ-63623872 at each sampling time point and for the derived plasma PK parameters. Statistics include sample size (n), mean, standard deviation (SD), %CV, geometric mean, median, minimum, and maximum.

For each subject treated with JNJ-63623872, JNJ-63623872 plasma concentration-time data will be graphically presented. Similarly, graphs of the mean plasma concentration-time profiles and overlay graphs with combined individual plasma concentration-time profiles will be produced. Pharmacokinetic parameters will be subjected to an exploratory graphical analysis in order to get a general overview.

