parameters observed in healthy subjects appear to be similar with or without prior inoculation of influenza A virus in a virus challenge model.

Clinical Efficacy

VX11-787-101 was a Phase 2a challenge study with a randomized, double-blind, placebo-controlled design. Four dose regimens of JNJ-63623872 or placebo were administered orally at 24 hours after viral inoculation and continued for 5 consecutive days: 100 mg once daily, 400 mg once daily, and single 900 mg or 1,200 mg loading dose followed by 600 mg once daily for 5 days (capsule). A total of 106 healthy subjects were enrolled and inoculated, 104 subjects received study drug (n=72 JNJ-63623872; n=32 placebo).

Healthy subjects were inoculated intranasally with 1.0 mL of a 50% tissue culture infective dose of 5.0 to 5.5 log₁₀/mL live influenza A/Wisconsin/67/2005 (H3N2) challenge strain virus on Day 0.

Results showed that JNJ-63623872 was effective in decreasing viral shedding in subjects with an active influenza A infection, with a concomitant reduction in symptoms.

- A statistically significant dose response trend was observed on the AUC of viral shedding by tissue culture assay (p=0.036) and quantitative reverse transcriptase polymerase chain reaction (qRT-PCR) (p=0.031).
- The 1,200/600-mg treatment group had a statistically significant reduction of the AUC of viral shedding by tissue culture (p=0.010) and by qRT-PCR (p=0.014) compared with placebo.
- The 1,200/600-mg treatment group had a statistically significant reduction of the AUC (p=0.040), peak (p=0.034), and duration (p<0.001) of patient-reported influenza-like symptom scores compared with placebo.
- The 1,200/600-mg treatment group had a statistically significant decrease in the duration (p=0.001) of patient-reported composite clinical symptom score compared with placebo.

These results suggest that JNJ-63623872 has the potential to be a novel treatment for patients with influenza A infection.

Clinical Virology

Population sequence analyses of the PB2 segment in subjects in study VX11-787-101 (healthy subjects challenged with influenza virus on Day 0, and treated with JNJ-63623872 for Days 1 through 5) identified a variant (PB2 M431I) that was observed in multiple subjects (n=4). This amino acid change confers a 57-fold decrease in sensitivity to JNJ-63623872 in in vitro studies but the virus had reduced replication capacity compared to wild type strains.

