4.4.2. Viral Genotype

Assessment of viral sequences will be done to determine amino-acid sequence changes that may be associated with resistance to JNJ-63623872 and/or oseltamivir. To that end, genotypic data for PB2, NA and optionally other genome segments of the influenza virus will be gathered.

All positions in the gathered regions will be analyzed.

The following 12 amino-acid positions in PB2 are of interest: Q306, F323, S324, F325, S337, H357, F363, K376, F404, Q406, M431, and N510.

The following resistance associated mutations in NA are of interest:

- For subtype H1N1: D199N, I223R, H275Y, and N295S
- For subtype H3N2: E119V, H274Y, R292K, and N294S

The list of positions of interest might be updated during the analysis.

A mutation is treatment-emerging at a specific (post-baseline) time-point if the amino-acid of the considered position is absent at screening/baseline and present at that time point.

The baseline is the collection of all polymorphisms present at any time point up to the first intake of study.

Data will be summarized using frequency tabulations (n and %). Displays and individual mutations should be presented overall and by influenza subtype category and for PB2 and NA separately. The following output will be provided:

- Baseline polymorphisms: number (%) of subjects with available genotype data, with any baseline polymorphism, and the number of subjects per polymorphism, for all polymorphisms, per treatment arm.
- Baseline polymorphisms: number (%) of subjects with any baseline polymorphism and with specific baseline polymorphisms at the positions of interest.
- Frequency tabulations for the presence of all emerging mutations overall post baseline.
- Frequency tabulations for the presence of all emerging mutations overall post baseline at positions of interest.
- Listing for genotype data per subject for all available time points including screening/baseline including viral load data (include influenza subtype and influenza subtype category).

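### SAP 4.4.1 judges phenotypic resistance at a last study visit that need not be post-baseline, drug-specific or on treatment, so the summary tables can dilute or omit emergence

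*SAP*

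**What the plan says.** Emergence of resistance by genotype and/or phenotype is a secondary objective (Protocol 2.1, SAP 1.1). For phenotype, SAP 4.4.1 plans these outputs:

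- "Emerging phenotypic resistance: descriptive statistics for FC in EC₅₀ and IC₅₀ value for JNJ-63623872 and oseltamivir respectively at baseline and the last study visit", together with the number of subjects per arm whose phenotype data are censored at those two points.
- A within-subject comparison: "Descriptive statistics for fold change ratio of last study visit versus baseline including geometric mean and 95% CI".
- A listing of viral load, EC50, IC50 and fold change "per subject and influenza subtype for all available time points including screening/baseline".

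The later of the two points is set by one sentence: "The last study visit is defined as the last time point for which an EC₅₀ and/or IC₅₀ result is available".

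The Protocol Synopsis (Secondary Endpoints, item 14) states which samples are tested: "Resistance testing will be performed on all baseline samples as well as on qRT-PCR-positive post-baseline samples". It adds that genotypic assays determine resistance to JNJ-63623872 and that phenotyping is at the sponsor's discretion.

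For genotype, SAP 4.4.2 ties emergence to post-baseline time points and plans "Frequency tabulations for the presence of all emerging mutations overall post baseline".

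**The concern.** A summary of emergence should compare baseline with something observed after dosing began, for the drug in question. The SAP sentence requires neither, and it sets no on-treatment window. Three things can follow.

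1. A subject whose only phenotype is the baseline one has baseline as the last available time point and contributes a ratio of 1.
2. Because either assay is enough to fix the visit, a last sample with only an oseltamivir IC50 becomes the last visit for both drugs. An earlier post-baseline JNJ-63623872 EC50 then drops out of the table.
3. The last sample can be off drug. A resistant population seen during dosing need not still be present then.

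What is at stake is how the phenotype tables of a descriptive secondary objective are read, and whether two programmers would build the same table from the text.

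**Working it through.** **The plan's own figure.** The only worked number in SAP 4.4.1 is its censoring example: "patient EC₅₀ = >20 nM, reference EC₅₀ = 4nM, Fold Change value >5". Fold change is the patient value over the reference, 20/4 = 5, so it reproduces.

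**The texts side by side.**

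- *Baseline as last.* Baseline samples are eligible for resistance testing whatever follows, but later samples only if qRT-PCR-positive, and phenotyping is optional. Subjects with only a baseline phenotype are therefore possible. The listing in SAP 4.4.1 counts screening/baseline among the available time points. SAP 3.1.6 duplicates the baseline record and assigns the copy to the treatment phase, so a treatment-phase filter alone would not remove it.
- *One visit for two drugs.* The definition names one visit per subject and accepts either assay. Nothing in it says the visit is chosen separately for EC50 and IC50.
- *Off-drug samples.* Dosing ends on Day 7 or the morning of Day 8 (Protocol 6). Central swabs run daily to Day 14 in hospital and are scheduled on Days 5, 8, 10 and 14 after discharge (Time and Events Schedules). SAP 3.1.1 ends the treatment phase 24 hours after the last intake, so for a subject who completes dosing the nominal Day 10 and Day 14 swabs fall outside it.

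**Illustration of dilution.** Inputs from Protocol 1.1 (Clinical Virology, Clinical Efficacy): the PB2 M431I variant was seen in 4 subjects of the challenge study, in which 72 received JNJ-63623872 (4/72 = 5.6%; the number sequenced is not given), and it lowers sensitivity 57-fold in vitro. Assumed, because the documents do not give them: p, the share of subjects with post-baseline results who show the 57-fold shift (5.6%, 10% or 20%), all others being unchanged; and b, the share of subjects in the ratio who are baseline-only (0 to 60%).

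The geometric mean ratio is 57^p with baseline-only subjects excluded and 57^(p(1−b)) with them entered at 1. For example, 57^0.0556 = 1.25 and 57^(0.0556 × 0.6) = 57^0.0333 = 1.14.

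| p | b = 0 | b = 20% | b = 40% | b = 60% |
|---|---|---|---|---|
| 5.6% | 1.25 | 1.20 | 1.14 | 1.09 |
| 10% | 1.50 | 1.38 | 1.27 | 1.18 |
| 20% | 2.24 | 1.91 | 1.62 | 1.38 |

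**Illustration of omission.** Let r be the assumed share of resistant subjects whose last sample no longer shows the shift. The resistant share at the last sample is p(1−r). At p = 10%, r of 25%, 50% and 75% gives 7.5%, 5.0% and 2.5%. If all 40 or all 60 planned active subjects had post-baseline phenotypes, r = 50% would show 2 rather than 4, or 3 rather than 6, resistant subjects. With r = 0 nothing is omitted.

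Even with b = 0 and r = 0, a 57-fold shift in 5.6% of subjects moves the geometric mean ratio only to 1.25. A mean-type summary is a weak detector of rare resistance at any visit, which is a reason to add a per-subject maximum.

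**The case against.** Much can be said for the plan.

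- **A later sample was probably meant.** The outputs speak of baseline and the last visit as two points, under a label about emergence, and name the drugs respectively, which suggests handling by assay. Display details sit in the Data Presentation Specifications, which are not available here. This makes the intended reading likely, but no rule in the SAP states it.
- **Nothing is lost from the report.** All phenotype time points are listed, and genotype emergence is counted at any post-baseline time for the same objective. This stands, and it confines the point to the summary tables.
- **The ratio is not the only quantitative summary.** Fold change at the last visit is also described, and the SAP 3.4 default statistics include the maximum, so a resistant last sample would show there. This stands, but that maximum covers last-visit results only, not earlier ones.
- **Genotype is the committed measure.** Phenotyping is discretionary, so the number of baseline-only subjects cannot be predicted. This also stands.

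A reader might go further and infer that emergent resistance will be understated, most of all in the active arm because it clears virus faster. The documents do not support that. They give no clearance rates and no count of baseline-only subjects. On outgrowth, Protocol 1.1 says only "but the virus had reduced replication capacity compared to wild type strains". Loss of the variant after dosing is plausible but not shown, and an off-drug sample can still carry resistance that arose on drug.

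A more dramatic contrast is also tempting. Three resistant subjects among 20 with post-baseline phenotypes give 57^(3/20) = 1.83, against 57^(3/60) = 1.22 if all 60 enter. It rests on assumed counts and on a resistant share of 3/20 = 15% among those tested, well above 5.6%.

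**Conclusion.** The definition in SAP 4.4.1 is incomplete in three respects that follow from its wording: no post-baseline condition, one visit for two assays, and no separation of on-treatment from later samples. The phenotype summaries can therefore dilute or omit emergent resistance; it is not established that they will. In the illustration the ratio falls from 1.25 to 1.14 at p = 5.6% and b = 40%, with no loss at b = 0. Only the 57-fold shift and the 4 of 72 come from the documents; b, r and the use of 5.6% for this trial are assumptions. Severity is minor, because the objective is descriptive, no hypothesis is tested, and the listing and genotype tables keep the information. It is still worth changing: the SAP already uses better conventions for genotype (any post-baseline time point) and for laboratory abnormalities (worst post-reference value per phase, SAP 4.3.2).

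**What to change.** In SAP 4.4.1:

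1. Define the last visit as the last post-baseline time point with a result, separately for JNJ-63623872 EC50 and oseltamivir IC50.
2. Exclude from the ratio for each drug any subject without a post-baseline result for that drug, and report their number by arm.
3. Add the highest post-baseline fold change per subject and drug, in line with the genotype rule.
4. Flag each result as inside the treatment phase already defined in SAP 3.1.1 (last intake plus 24 hours) or later.

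The cost is SAP wording and one extra table; no new data are needed. The ratio will rest on fewer subjects, so its confidence interval will be wider. Those subjects are also the ones still PCR-positive after dosing began, so the counts by arm are needed to read it. The maximum tends to rise with the number of positive samples per subject, so it should be shown beside the last-value summary rather than in its place.

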4.4.2. Viral Genotype

Assessment of viral sequences will be done to determine amino-acid sequence changes that may be associated with resistance to JNJ-63623872 and/or oseltamivir. To that end, genotypic data for PB2, NA and optionally other genome segments of the influenza virus will be gathered.

All positions in the gathered regions will be analyzed.

The following 12 amino-acid positions in PB2 are of interest: Q306, F323, S324, F325, S337, H357, F363, K376, F404, Q406, M431, and N510.

The following resistance associated mutations in NA are of interest:

- For subtype H1N1: D199N, I223R, H275Y, and N295S
- For subtype H3N2: E119V, H274Y, R292K, and N294S

The list of positions of interest might be updated during the analysis.

A mutation is treatment-emerging at a specific (post-baseline) time-point if the amino-acid of the considered position is absent at screening/baseline and present at that time point.

The baseline is the collection of all polymorphisms present at any time point up to the first intake of study.

Data will be summarized using frequency tabulations (n and %). Displays and individual mutations should be presented overall and by influenza subtype category and for PB2 and NA separately. The following output will be provided:

- Baseline polymorphisms: number (%) of subjects with available genotype data, with any baseline polymorphism, and the number of subjects per polymorphism, for all polymorphisms, per treatment arm.
- Baseline polymorphisms: number (%) of subjects with any baseline polymorphism and with specific baseline polymorphisms at the positions of interest.
- Frequency tabulations for the presence of all emerging mutations overall post baseline.
- Frequency tabulations for the presence of all emerging mutations overall post baseline at positions of interest.
- Listing for genotype data per subject for all available time points including screening/baseline including viral load data (include influenza subtype and influenza subtype category).

4.5. Health Care

The number of subjects admitted to the Intensive Care Unit (ICU) after baseline will be tabulated.

The length of ICU stay for subjects transferred to the ICU after baseline is calculated as:

$$\text{End date in ICU} - \text{Start date in ICU} + 1.$$

If a subject has multiple periods in the ICU the durations for these separate stays in the ICU will be summed.

Descriptive statistics of the duration in the ICU will be shown for all subjects that were admitted to the ICU after baseline.

References

Royal College of Physicians of London. (2012) National early warning score (NEWS): standardising the assessment of acute-illness severity in the NHS.. www.rcplondon.ac.uk/resources/national-earlywarning-score-news

Guideline, I. H. T. (2006). The clinical evaluation of QT/QTc interval prolongation and proarrhythmic potential for non-antiarrhythmic drugs E14. Recommended for adoption at Step, 4

White, I. R., Royston, P., & Wood, A. M. (2011). Multiple imputation using chained equations: issues and guidance for practice. *Statistics in medicine*, 30(4), 377-399.

World Health Organization. (2003) "WHO toxicity grading scale for determining the severity of adverse events."

Appendix 1 Anticipated Events and Anticipated Event Groups

Table 10 shows an overview of the anticipated event groups with group number.

Table 11 indicates which adverse event preferred terms (MedDRA PT) are Anticipated Events (AnE) and Closely Related Medical Events (ME). These adverse events will be classified as an Anticipated Event according to the protocol term and are grouped into Anticipated Event Groups. One adverse event can be added to one or two groups according to Table 11.

Table 10: Anticipated Event groups

Group Number	Grouped Term
Group 1	Infections and infestations
Group 2	Bacterial Pneumonia
Group 3	Bronchitis
Group 4	Sinus infection
Group 5	Ear infection
Group 6	Worsening of asthma, asthma attack
Group 7	COPD exacerbation
Group 8	Complications of sickle cell disease, sickle cell crisis
Group 9	Diabetic complications
Group 10	Acute Respiratory Distress Syndrome (ARDS)

Table 11: Anticipated Events (AnE) and Closely Related Medical Events (ME).

Protocol Term Anticipated Event	AnE	ME	MedDRA PT	MedDRA Code*	Anticipated Event Grouped Term	Group Number
Bacterial pneumonia			Pneumonia bacterial	10060946	Infections and infestations/Bacterial Pneumonia	1/2
Bacterial pneumonia			Enterobacter pneumonia	10054218	Infections and infestations/Bacterial Pneumonia	1/2
Bacterial pneumonia			Pneumonia haemophilus	10035702	Infections and infestations/Bacterial Pneumonia	1/2
Bacterial pneumonia			Pneumonia staphylococcal	10035734	Infections and infestations/Bacterial Pneumonia	1/2

Bacterial pneumonia			Pneumonia streptococcal	10035735	Infections and infestations/Bacterial Pneumonia	1/2
Bronchitis			Bronchitis	10006451	Infections and infestations/Bronchitis	1/3
Bronchitis			Bronchitis bacterial	10061736	Infections and infestations/Bronchitis	1/3
Bronchitis			Bronchitis haemophilus	10006460	Infections and infestations/Bronchitis	1/3
Sinus infection			sinusitis ^a	10040753	Infections and infestations/Sinus infection	1/4
Sinus infection			Acute sinusitis ¹	10001076	Infections and infestations/Sinus infection	1/4
Sinus infection			Chronic sinusitis	10009137	Infections and infestations/Sinus infection	1/4
Sinus infection			Viral sinusitis	10051513	Infections and infestations/Sinus infection	1/4
Ear infection			Ear infection	10014011	Infections and infestations/ Ear infection	1/5
Ear infection			Middle ear effusion	10062545	Infections and infestations/ Ear infection	1/5
Ear infection			Otitis externa	10033072	Infections and infestations/ Ear infection	1/5
Ear infection			Otitis media	10033078	Infections and infestations/ Ear infection	1/5
Ear infection			Otitis media acute	10033079	Infections and infestations/ Ear infection	1/5
Worsening of asthma, asthma attack ^b			Asthma	10003553	Worsening of asthma, asthma attack	6
Worsening of asthma, asthma attack ²			Asthmatic crisis	10064823	Worsening of asthma, asthma attack	6
COPD exacerbation ^c			Chronic obstructive pulmonary disease	10009033	COPD exacerbation	7
COPD exacerbation ³			Emphysema	10014561	COPD exacerbation	7
Complications of sickle cell disease, sickle cell crisis ^d			Sickle cell anaemia	10040641	Complications of sickle cell disease, sickle cell crisis	8
Complications of sickle cell disease, sickle cell crisis ⁴			Acute chest syndrome	10051895	Complications of sickle cell disease, sickle cell crisis	8

^a Infectious etiology only

^b Please note that asthma aggravated codes to a PT of asthma. These PTs will be considered as anticipated events only if the subjects have documented those conditions (such as: asthma, COPD, Sickle cell disease, or diabetes) before enrolling the study.

^c Please note that chronic obstructive airways disease exacerbated codes to a PT of chronic obstructive pulmonary disease. These PTs will be considered as anticipated events only if the subjects have documented those conditions (such as: asthma, COPD, Sickle cell disease, or diabetes) before enrolling the study.

^d These PTs will be considered as anticipated events only if the subjects have documented those conditions (such as: asthma, COPD, Sickle cell disease, or diabetes) before enrolling the study.

Complications of sickle cell disease, sickle cell crisis ⁴			Pain	10033371	Complications of sickle cell disease, sickle cell crisis	8
Complications of sickle cell disease, sickle cell crisis ⁴			Ischaemic stroke	10061256	Complications of sickle cell disease, sickle cell crisis	8
Complications of sickle cell disease, sickle cell crisis ⁴			Embolic stroke	10014498	Complications of sickle cell disease, sickle cell crisis	8
Complications of sickle cell disease, sickle cell crisis ⁴			Deep vein thrombosis	10051055	Complications of sickle cell disease, sickle cell crisis	8
Complications of sickle cell disease, sickle cell crisis ⁴			Pulmonary embolism	10037377	Complications of sickle cell disease, sickle cell crisis	8
Complications of diabetes mellitus, diabetic ketoacidosis ^e			Diabetic complications	10061104	Diabetic complications	9
Complications of diabetes mellitus, diabetic ketoacidosis ⁵			Diabetic ketoacidosis	10012671	Diabetic complications	9
Complications of diabetes mellitus, diabetic ketoacidosis ⁵			Diabetes mellitus ^f	10012601	Diabetic complications	9
Complications of diabetes mellitus, diabetic ketoacidosis ⁵			Diabetic ketoacidotic hyperglycaemic coma	10012672	Diabetic complications	9
Complications of diabetes mellitus, diabetic ketoacidosis ⁵			Hypoglycaemia	10020993	Diabetic complications	9
Acute Respiratory Distress Syndrome (ARDS)			Acute respiratory distress syndrome	10001052	Acute Respiratory Distress Syndrome (ARDS)	10
Acute Respiratory Distress Syndrome (ARDS)			Acute respiratory failure ^g	10001053	Acute Respiratory Distress Syndrome (ARDS)	10

^e These PTs will be considered as anticipated events only if the subjects have documented those conditions (such as: asthma, COPD, Sickle cell disease, or diabetes) before enrolling the study.

^f Please note that diabetes mellitus aggravated and diabetes mellitus exacerbated codes to a PT of diabetes mellitus

^g This event will be considered anticipated only if it occurs in the context of ARDS

